7.1. Efficacy Analyses

The following analyses will be conducted for the endpoints of antitumor activity in the tumor response-evaluable population and for PFS and TTF in the FAS population. For the selected endpoints, the same analyses will also be conducted by country.

7.1.1. Antitumor Activity

7.1.1.1 Best Overall Response

- The proportion of subjects with each best overall response will be calculated in each treatment arm.

7.1.1.2 ORR

- The ORR and its 95% confidence interval will be estimated in each treatment arm.
- The ORR will be compared between the treatment arms by Fisher's exact test and Cochran–Mantel–Haenszel test stratified by the allocation adjustment factors. For the allocation adjustment factors, data entered in the CRF will be used.
- For each baseline characteristic factor listed in Table 5-7 in Section “5.2.2 Patient Baseline Characteristics,” the ORR and its 95% confidence interval will be estimated in each treatment arm.
- The ORR analyses specified above will also be conducted by country. In the stratified Cochran–Mantel–Haenszel test, the allocation adjustment factors other than the country will be used as strata.

7.1.1.3 DCR

- The DCR will be analyzed in each treatment arm in the same manner as specified in Section “7.1.1.2 ORR.”

7.1.1.4 Time to Response

- Cycles in which overall response has first been determined to be CR or PR after the start of study treatment will be tabulated, and the summary statistics of the number of days to CR or PR will be presented in each treatment arm.

7.1.1.5 Duration of Overall Response

- The following analyses will be conducted in subjects with the best overall response of CR or PR in the tumor response-evaluable population:
- The survival curve of the duration of overall response, MST, and 95% confidence interval will be estimated in each treatment arm. In addition, the number of subjects at risk at 3-month intervals, cumulative event-free rate, and median follow-up period and their 95% confidence intervals will be presented, and the analyses specified above will also be conducted by country. Duration of complete response
- In subjects with the best overall response of CR in the tumor response-evaluable population, the analyses specified in Section “7.1.1.5 Duration of Overall Response” will be conducted.

7.1.2. PFS

- Progression-free survival will be analyzed in the same manner as specified in Section “6. Primary Endpoint Analyses” (excluding the analyses of RMST and between-group difference in MST). In

the analyses using the allocation adjustment factors, only data entered in the CRF will be used with a confidence level of 95% for all confidence intervals.

- In the enrolled population, the same analyses will be conducted.

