16.3.3.1 Efficacy Endpoints

(1) Overall Response Rate (ORR)

Following analyses will be performed in TR population.

- In each study treatment, best overall responses will be summarized and ORRs with 95% confidence interval will be estimated. The treatment comparison will be done using Fisher's exact test.
- In each study treatment, onset date, duration of response (duration of overall response and duration of overall complete response) for antitumor effect will be summarized in patients with responses.

(2) Disease Control Rate (DCR)

- In each study treatment and TR population, DCR based on the best overall response will be estimated. The treatment comparison will be done by Fisher's exact test.

(3) Progression Free Survival (PFS)

- In each study treatment and FAS population, survival curves of PFS will be estimated and MST with 95% confidence interval using the Kaplan-Meier method will be presented. Otherwise the number at risk and cumulative event free rate every three months will be presented.
- PFS in the FAS will be compared between the two study treatment arms using stratified log-rank test by three stratification factors. In addition, hazard ratio of PFS with 95% confidence interval will be estimated by CPH model with the study drug as covariates.

(4) Time to Treatment Failure (TTF)

- In FAS population, TTF analyses will be performed by the same ways as PFS analyses.

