17.1 Preparation of CRF

The investigator shall be provided with standardized eCRFs and shall ensure that all data from patient visits are promptly entered into the eCRFs in accordance with the specific instructions given.

Investigators will be provided with detailed eCRF Completion Guidelines that will identify the required data points to be collected, how to document them, and when the data should be documented.

It is the responsibility of the investigator to maintain adequate and accurate eCRFs to record (according to the eCRF Completion Guidelines) all observations and other data pertinent to the clinical trial obtained during scheduled or unscheduled visits. All eCRFs should be fully completed to ensure accurate data interpretation.

The investigator should record all the data on eCRFs in accordance with time limit in the following items (Except the sponsor request to stop recording the data);

- Patient background : Within 14 days after randomization
- Administration record : Within 14 days after last administration of each cycle
- Hematology, serum chemistry, urinalysis : Within 14 days after the test date
- Survival, post treatment : 14 days after getting the information
- Other items : Within 14 days after end of treatment

The computerized handling of the data by the sponsor after receipt of the eCRFs may generate additional requests via electronic queries or other means to which the investigator is obliged to respond by confirming or modifying the data questioned. These requests with their responses will be appended to the eCRFs held by the investigator and the sponsor.

18. Protocol Compliance, Deviation and Amendment

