6.1. Primary Analysis for Primary Objective

- The superiority of TAS-118/L-OHP to S-1/CDDP with respect to OS will be tested in the FAS population. As the test method, a stratified log-rank test will be conducted according to the following allocation adjustment factors: ECOG PS (0, 1), measurable lesion (1: yes, 0: no), and country (1: Japan, 0: Korea). If the data on ECOG PS and measurable lesion at randomization differ from the data entered in the CRF, the data obtained at randomization will be used.

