7.1.3. TTF

- Time to treatment failure will be analyzed in the same manner as specified in Section “6. Primary Endpoint Analyses” (excluding the analyses in the enrolled population and the analyses of RMST and between-group difference in MST). In the analyses using the allocation adjustment factors, only data entered in the CRF will be used with a confidence level of 95% for all confidence intervals.

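### PFS and TTF are stratified only by CRF-entered factors, while OS uses the values at randomization; align them and keep CRF strata as the sensitivity analysis

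*SAP*

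**What the plan says.** **OS.** SAP 6.1 tests OS with a log-rank test stratified by ECOG PS, measurable lesion and country. Where the two sources disagree on PS or measurable lesion, "the data obtained at randomization will be used". SAP 6.2 repeats the test with CRF strata and also without strata. SAP 6.3 fits Cox models with both sources.

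**PFS and TTF.** SAP 7.1.2 and 7.1.3 import Section 6 and then restrict the source. For PFS, in "the analyses using the allocation adjustment factors, only data entered in the CRF will be used"; for TTF, "In the analyses using the allocation adjustment factors, only data entered in the CRF will be used".

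**ORR and DCR.** SAP 7.1.1.2 compares ORR by Fisher's exact test and by a stratified CMH test: "For the allocation adjustment factors, data entered in the CRF will be used". DCR follows ORR: "The DCR will be analyzed in each treatment arm in the same manner as specified in Section" 7.1.1.2.

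**Protocol.** Section 16.3.3.1 says "PFS in the FAS will be compared between the two study treatment arms using stratified log-rank test by three stratification factors" and does not say which record supplies the factor values.

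**CRF fields and timing.** SAP 5.2.2 takes PS from the vital-signs page tied to the time of randomization, and measurable lesion from the baseline imaging page (present if a target lesion was recorded). It also excludes missing baseline values from statistical tests. Protocol 17.1 sets early entry deadlines for patient background, dosing records, laboratory tests, survival and post-treatment. For the rest it says "Other items : Within 14 days after end of treatment".

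**The concern.** The strata in a stratified test should be those under which patients were allocated, with values fixed before the arm was known. The IWRS values meet that description: the minimization needs them for every patient before it assigns a treatment. CRF values need not meet it. Protocol Table 11.1-1 lists ECOG PS and tumor measurement separately from patient background, so neither falls under an early entry deadline. The trial is open-label, so they may be entered or corrected by people who know the arm.

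Two things are lost. First, Section 6 alone would give PFS a main test on randomization strata and a sensitivity test on CRF strata. The restriction to CRF data makes these one test, so nothing checks whether the source matters. Second, a patient with a missing CRF factor can drop out of the stratified test. That is most plausible in the enrolled-population PFS analysis, which includes patients who were never treated.

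At stake is the stratified PFS and TTF result, not the OS conclusion.

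**Working it through.** No figure in the plan depends on this point, so there is none to reproduce. The check has three parts.

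**1. Sources side by side**

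| Endpoint | Main stratified analysis | Other source | Analysis without strata |
|---|---|---|---|
| OS | Randomization (SAP 6.1) | CRF (6.2, 6.3) | Log-rank (6.2) |
| PFS | CRF only (7.1.2) | None | Log-rank, imported from 6.2 |
| TTF | CRF only (7.1.3) | None | Log-rank, imported from 6.2 |
| ORR, DCR | CRF, CMH (7.1.1.2, 7.1.1.3) | None | Fisher's exact |

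SAP 6.1 treats only ECOG PS and measurable lesion as able to differ between sources; country is not in question.

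**2. ORR and DCR**

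The tumor response-evaluable population (SAP 3.2) requires at least one target lesion, and SAP 5.2.2 equates a target lesion with measurable disease. The CRF factor is therefore always yes here. The CMH test has at most 2 (PS) × 2 (country) = 4 strata, and only PS can differ in effect. If the randomization value of measurable lesion were used instead, its no stratum would hold only discordant patients, split again by PS and country.

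**3. Does the source matter to the test?**

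A simulation under the null used a stratified log-rank statistic, Z = ΣΣ(g − p) / √(ΣΣ p(1 − p)). The sums run over strata and events, g marks the arm of the patient with the event, and p is that arm's share of patients at risk.

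Assumptions, none from the documents except the FAS target of 650: PS 1 in 45%; PS hazard ratio 1.3 or 1.6; measurable lesion in 80% with hazard ratio 1.2; half the patients in each country; median PFS 6 months; balanced allocation within strata in place of minimization; 3,000 runs per setting. Simulation error at 5% is 1.96 × √(0.05 × 0.95 / 3000) = ±0.8 points; at 2.5% it is ±0.6 points.

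*Random discordance.* The IWRS holds random PS errors in 5% or 10% of patients and the CRF corrects them.

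| Strata used | Two-sided rejection at nominal 5% |
|---|---|
| No discordance | 5.1% to 5.3% |
| Randomization values | 5.1% to 5.5% |
| CRF values | 4.6% to 5.4% |

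All are compatible with 5%. Neither source biases the test.

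*Arm-dependent recording.* A share of one arm's PS 0 patients is recorded as PS 1 in the CRF, regardless of outcome. That arm has about 325 × 0.55 = 179 PS 0 patients.

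| Share recoded | Patients | One-sided error in that arm's favour (PS HR 1.3; 1.6) | Mean Z (PS HR 1.3; 1.6) |
|---|---|---|---|
| 0% | 0 | 2.7%; 2.4% | 0.01; 0.00 |
| 5% | 9 | 3.3%; 3.9% | −0.11; −0.19 |
| 10% | 18 | 4.3%; 5.2% | −0.21; −0.38 |
| 20% | 36 | 5.2%; 8.0% | −0.36; −0.63 |

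The standard error of a mean Z is 1/√3000 = 0.02, so the shifts are real under these assumptions. At 5% recoding with PS HR 1.3, the rise in error rate by itself is close to simulation noise.

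A separate, smaller simulation (650 patients, PFS HR 0.8, 150 replicates) took random discordance of 2%, 5% or 8% in both factors. The stratified Z then differed between the two sets of strata with a standard deviation of 0.12, 0.19 or 0.23. That shows how far the reported result can depend on the source. It does not show bias.

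**The case against.** The strongest reply is that the CRF values are baseline data, checked against source, and may be the more accurate record. Much of this stands.

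- A reader might infer that post-randomization data define the strata. The documents do not say so. Both CRF fields are baseline pages, the scan must fall within 21 days before randomization, and the 17.1 deadline governs entry, not assessment. PS is a chart item (protocol 19.1), baseline images go to the sponsor (11.1.1), and monitors compare CRF with source (19.2). What remains is an opportunity. Image-evaluation records may be entered directly in the CRF as source data (19.1). SAP 5.2.2 also takes the latest value before treatment, and dosing may start up to 8 days after randomization, although the PS page title points to randomization.
- A reader might infer an undeclared change from the protocol. Protocol 16.3.3.1 names three factors and no data source, and Section 16 leaves technical detail to the SAP. No deviation is shown.
- A reader might infer that PFS cannot be compared with OS. It can: SAP 6.2 and 6.3 already analyze OS with CRF strata.
- The choice is prespecified, and SAP Section 8 requires version 1 to be final before receipt of the CRF data or allocation key used for the results. That guards against choosing the source after seeing results. It does not guard against arm-aware entry.

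Greater accuracy of the CRF would be an argument for OS too, where the SAP chose the other order. The inconsistency therefore stays unexplained.

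**Conclusion.** The point holds as a modest improvement. PFS and TTF have no stratified analysis by the randomized strata and no check on the data source, and the SAP does not say why they differ from OS. Random discordance would do no harm to the type I error. Under the stated assumptions, arm-dependent recoding of 5% to 20% of one arm's PS 0 patients would raise a 2.5% one-sided error to between 3.3% and 8.0%. The documents give no discordance rate and no sign that such recoding occurred, so this range illustrates the mechanism and is not an estimate for this trial.

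The consequence is limited further because the endpoints are secondary, no alpha-controlled testing order is set for them, and unstratified log-rank and Fisher tests do not use the strata. For ORR and DCR the point reaches only the CMH test, and within it only ECOG PS. The reading that CRF entry can be late rests on PS and baseline imaging falling under the residual category in protocol 17.1.

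**What to change.** - **SAP 7.1.2 and 7.1.3:** use the randomization (IWRS) values of ECOG PS and measurable lesion, with country, for the main stratified log-rank and Cox analyses. Keep the CRF strata as the sensitivity analysis, as for OS.
- **SAP 7.1.1.2 and 7.1.1.3:** stratify the CMH test by the randomization value of ECOG PS and by country, and drop measurable lesion, since every patient in that population has a target lesion. In the by-country analyses, ECOG PS is then the only stratum. Fisher's test is unchanged.

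The cost is one extra sensitivity run and a change of variables. The randomization variables (MLIWN, PSIWN, CNTRYIWN) are already in the sample code of SAP 5.2.4.12. If version 1 of the SAP is already final, Section 8 requires the change and its reason to be recorded. No event number, significance level or sample size changes.

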7.1.3. TTF

- Time to treatment failure will be analyzed in the same manner as specified in Section “6. Primary Endpoint Analyses” (excluding the analyses in the enrolled population and the analyses of RMST and between-group difference in MST). In the analyses using the allocation adjustment factors, only data entered in the CRF will be used with a confidence level of 95% for all confidence intervals.

7.1.4. Tumor Shrinkage Rate

- The distributions of maximum tumor shrinkage rate and tumor shrinkage rate at 6 and 12 weeks after entry will be illustrated in a waterfall plot in each treatment arm.
- The summary statistics will be presented for the maximum tumor shrinkage rate, tumor shrinkage rates at 6 and 12 weeks after entry and at the last imaging assessment, and tumor shrinkage rate at the last imaging assessment in subjects who discontinued the study because of PD in each treatment arm. The maximum tumor shrinkage rate will be compared between the treatment arms by a Wilcoxon test.
- The proportion of subjects with tumor shrinkage of $\geq 20\%$ at 6 weeks after entry will be presented and compared between the treatment arms by Fisher’s exact test.

7.2. Safety Analysis

The following analyses will be conducted in the AT population. These analyses except listings will also be conducted by country. The listings will be provided in the enrolled population.

7.2.1. Adverse Events and Adverse Drug Reactions

- The number and proportion of subjects with adverse events and adverse drug reactions will be calculated by MedDRA SOC and PT and grade in each treatment arm. For grade 2 or higher events, grade 3 or higher events, and events with an incidence of $\geq 10\%$ in either arm (an incidence of $\geq 5\%$ for adverse drug reactions), the number and proportion of subjects will also be calculated by MedDRA SOC and PT and grade.
- According to ECOG PS entered in the CRF and age (< 75 years), the number and proportion of subjects with adverse events and adverse drug reactions will be calculated by MedDRA SOC and PT and grade in each treatment arm.
- The number and proportion of subjects with adverse events leading to discontinuation (subjects with adverse events recorded in “Treatment Discontinuation” of the CRF) will be calculated by MedDRA SOC and PT in each treatment arm.
- The number and proportion of subjects with adverse events leading to interruption of TAS-118 or S-1 within a cycle will be tabulated by MedDRA PT in each treatment arm.
- The number and proportion of subjects with adverse events leading to the interruption of L-OHP or CDDP will be tabulated by MedDRA SOC and PT in each treatment arm.
- The number and proportion of subjects with adverse events leading to a skip of L-OHP or CDDP will be tabulated by MedDRA SOC and PT in each treatment arm.
- The number and proportion of subjects with adverse events leading to dose reduction in TAS-118, S-1, L-OHP, or CDDP will be tabulated by MedDRA SOC and PT in each treatment arm.
- The number and proportion of subjects with adverse events leading to prolongation of the TAS-118 or S-1 recovery period will be tabulated by MedDRA SOC and PT in each treatment arm.
- The number and proportion of subjects with serious adverse events will be tabulated by MedDRA SOC and PT in each treatment arm. Serious adverse drug reactions will also be analyzed in the same manner.
- A list of adverse event type, grade, time of onset, causality, course, treatment, and other information will be created in the enrolled population.
- For serious adverse events, a list of grade, outcome, date of outcome, seriousness, causality, and other information will be created in the enrolled population.

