
	premenopausal, less than 1 year after last menses, more than 1 year with no menses due to medical causes, or not permanently sterilized and so on.
Treatment Regimens:	
[Arm A (TAS-118/L-OHP)] L-OHP will be administered intravenously at dose of 85 mg/m² on day 1, and TAS-118 will be administered 30-60 mg orally twice daily for 7 days (day 1 through day 7), repeated every 2 weeks. Treatment will be continued during the study period unless any of Study Treatment Discontinuation Criteria (see Section 13.1.1) is met.
 
[Arm B (S-1/CDDP)] CDDP will be administered intravenously at dose of 60 mg/m² on day 1 (Korea) or day 8 (Japan), and S-1 will be administered 40-60 mg orally twice daily for 21 days (day 1 through day 21), repeated every 5 weeks (rest period can be shorten from 14 days to 7 days). Treatment will be continued during the study period unless any of Study Treatment Discontinuation Criteria (see Section 13.1.1) is met.

Registration	Central registration
Study drugs	TAS-118 (granules): 30 mg, 40 mg, 50 mg, 60 mg L-OHP (infusion solution): 100 mg S-1 (capsule): 20 mg, 25 mg CDDP (infusion solution): 50 mg
Allocation	Treatment assignment will be done centrally using a dynamic allocation method (minimization method) via an IWRS stratified by: 
 - ECOG PS: (0, 1) - Measurable lesion: (Yes, No) - Country: (Japan, Korea)
Observation/examination items and study schedule	See Tables in the following page.
Evaluation method	
Evaluation of anti-tumor effects
 
 - RECIST criteria version 1.1 
Evaluation of adverse events
 
 - CTCAE version 4.03
Planned Sample Size:	686 patients will be enrolled in the study using a treatment allocation of 1:1 (TAS-118/L-OHP: S-1/CDDP).
Study period	December 2014 to May 2020

Table 1 A Study Schedule Arm A (TAS-118/L-OHP)

Procedure	Pretreatment Period				Study Treatment Period		Post-treatment Follow-up Period			
	within 28 days prior to randomization	within 21 days prior to randomization	within 14 days prior to randomization	within 7 days prior to Day 1 of the first treatment cycle ^e	Arm A		End of Treatment ^j (+14 days)	Safety Follow-up ^k 30 days after last dose of study treatment (+14 days)	Tumor Follow-up Every 6 weeks (+/- 1 week)	Survival Follow-up Every 12 weeks (+/- 2 weeks)
					Day 1	Before Initiation of next treatment cycle ^{h,i} Day15 (Day 14 to 18)				

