2.4 Rationale for considering the new therapy as promising

Efficacy of TAS-118 and L-OHP against gastric cancer

In the [REDACTED] for patients with unresectable, advanced, recurrent gastric cancer conducted in Japan (see section 2.3.2.4), RR was highest at 66% for the S-1/LV/L-OHP group and PFS was 8.3 months, and OS was 18.4 months. On the other hand, RR was 46%, PFS was 5.6 months and OS was 12.6 months for one of the standard therapy, S-1/CDDP group, and S-1/LV/L-OHP group showed high efficacy. In addition, the efficacy of S-1/CDDP group was similar to other studies^{9, 13, 24}. Therefore S-1/LV/L-OHP was suggested as promising regimen to show high efficacy. Regarding safety, tolerability was also

shown. From these results, TAS-118/L-OHP therapy using TAS-118 containing S-1 and LV is expected to be promising as the first-line therapy in patients with gastric cancer.

3. GCP Compliance and Ethical Conduct of the Study

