10.1.2.1 Arm A (TAS-118/L-OHP)

L-OHP will be administered on Day 1, and TAS-118 will be administered orally twice daily in a administration period from Day 1 through Day 7 followed by a recovery period from Day 8 through Day 14. This regimen is to be repeated every 2 weeks until study treatment discontinuation criteria (Section 13.1.1). If TAS-118 administration is initiated from evening on Day 1, it will be continued until morning on Day 8, and recovery period will be from evening on Day 8 through morning on Day 15 (see Figure 10.1.2.1-1).

- A recovery period is not allowed to be shortened (e.g. even if the dosing is interrupted due to some reasons, such as adverse events after the morning of Day 6, the subsequent dosing should be started as a new treatment cycle after the morning/evening meal on Day 15).
- Any unused doses are not allowed to be administered in a recovery period (see Figure 10.1.2.1-2).
- If any of dose initiation criteria (see Table 10.1.3.1-1) for L-OHP did not meet, administration of L-OHP may be skipped and start each treatment cycle only with TAS-118.

[figure not shown]

Figure 10.1.2.1-1 Study regimen of TAS-118/L-OHP

[figure not shown]

Figure 10.1.2.1-2 Study regimen of TAS-118

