13.1 Discontinuation criteria for individual subject

13.1.1 Study Treatment Discontinuation Criteria

Discontinue the study treatment if any of the following occur:

- Disease progression defined by RECIST version 1.1
- Patient has an adverse event (AE) that in the opinion of the investigator (subinvestigator) requires the study treatment to be discontinued
- Patient has not taken the study drug for more than 28 consecutive days
- Application for curative surgery due to tumor shrinkage
- Patient has a critical protocol deviation
- Pregnancy
- Patient request to discontinue the study treatment
- The investigator (subinvestigator) concludes that the patient needs to discontinue the study treatment
- Study is completed

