5.1.2. Safety Endpoints

5.1.2.1 Adverse Events and Adverse Drug Reactions

An adverse event (AE) is any untoward medical condition sign, symptom, or disease that occurs in a subject while participating in this study and does not necessarily have a causal relationship with the study drug.

Treatment-emergent adverse events are AEs that occur from the initiation of any study medication administration and do not necessarily have a causal relationship with the study drug.

Any untoward medical sign, symptom, or disease that occurs outside the period of safety follow-up (30 days after the last dose of study medication or until the start of new antitumor therapy, whichever comes first) is not considered an AE. If any AEs are observed after the safety follow-up period has ended, only those AEs suspected to have a causal relationship with the study drug will be recorded in the CRF.

The analysis of AEs will be based on treatment-emergent adverse events.

Adverse drug reactions in this study are defined as adverse events (including laboratory abnormalities) determined to have a reasonable possibility of a causal relationship with the study drug.

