5.2.1.2 Handling of Missing Data and Abnormal Values

No imputation of missing data will be performed. All data accepted at each time point will be used for the analysis. The proportion of subjects with adverse events and other proportions will be calculated using the analysis population as the denominator.

All data measured will be used for the analysis unless the cause of abnormalities is obvious, such as laboratory abnormalities caused by hemolysis during blood collection. If there are abnormalities to be

excluded from the analysis, these values will be identified, and the reason for exclusion will be justified.

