5.2.3.5 Estimation Methods

(1) Confidence interval of proportions

The confidence interval of ORR, DCR, and the proportion of subjects with adverse events will be calculated using the F distribution-based method proposed by Clopper and Pearson (1934).⁸⁾

The upper limit of confidence interval P_U and the lower limit of confidence interval P_L will be estimated using the following formulas, where P is a proportion, X is the number of subjects with events, N is the number of subjects in the analysis population, and α is a two-sided significance level:

$$P = X/N$$

$$P_U = \frac{v_1 F_{v_1, v_2}(\alpha/2)}{v_2 + v_1 F_{v_1, v_2}(\alpha/2)}, v_1 = 2(X + 1), v_2 = 2(N - X)$$

$$P_L = \frac{v_2}{v_2 + v_1 F_{v_1, v_2}(\alpha/2)}, v_1 = 2(N - X + 1), v_2 = 2X$$

(2) Estimation of survival curves

The survival time function $S(t_j)$ will be estimated using the following formula based on the Kaplan–Meier method, where $t_1 < t_2 < \dots < t_N$ is the time of event onset in subject $j = 1, \dots, N$, n_j is the number of subjects at risk at time t_j , and d_j is the number of subjects with events:

$$\hat{S}(t_N) = \prod_{j=1}^N \left(1 - \frac{d_j}{n_j}\right)$$

(3) Confidence interval of MST

The confidence interval of MST will be calculated using the method based on the sign test for censored data.⁹⁾

The standard error of survival time function $S(t_j)$ will be estimated using the following formula:

$$\hat{\sigma}(\hat{S}(t_N)) = \hat{S}(t_N) \sqrt{\sum_{j=1}^N \frac{d_j}{n_j(n_j - d_j)}}$$

The confidence interval of MST is defined as the time of event onset within the following interval, where α is a two-sided significance level:

$$\left\{t: (1 - \hat{S}(t) - 0.5)^2 \leq \chi_1^2(\alpha) \hat{\sigma}^2(\hat{S}(t))\right\}$$

(4) Confidence interval of hazard ratios

The covariance matrix of a regression coefficient estimate $\hat{\boldsymbol{\beta}}$ is expressed using the following formula, where $l(\boldsymbol{\beta})$ is a log-likelihood function:

$$\hat{\mathbf{V}}(\hat{\boldsymbol{\beta}}) = - \left[\frac{\partial^2 l(\hat{\boldsymbol{\beta}})}{\partial \boldsymbol{\beta} \partial \boldsymbol{\beta}'} \right]^{-1}$$

Ties in survival time, if any, will be processed using the Breslow method.

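### Adverse-event frequency is planned only as crude proportions while treatment length depends on outcome, so unequal time on treatment could distort the comparison of toxicity; fixed-time incidence should be added.

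*SAP*

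**What the plan says.** **AE measure.** SAP 7.2.1 sets the main table: "The number and proportion of subjects with adverse events and adverse drug reactions will be calculated by MedDRA SOC and PT and grade". Its tables for serious AEs and for AEs leading to discontinuation, interruption, skipping, dose reduction or a longer recovery period take the same form. SAP 5.2.1.2 fixes the denominator: "The proportion of subjects with adverse events and other proportions will be calculated using the analysis population as the denominator". SAP 5.2.3.5 adds exact intervals for these proportions. Protocol 16.3.3.3 plans rates, maximum grades and listings. Neither document describes a person-time rate, a time-to-first-AE analysis or an AE proportion in a fixed window.

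**Treatment length.** The Protocol Synopsis says for each arm: "Treatment will be continued during the study period unless any of Study Treatment Discontinuation Criteria (see Section 13.1.1) is met". The first criterion in Protocol 13.1.1 is "Disease progression defined by RECIST version 1.1"; eight others follow, including an AE, more than 28 consecutive days without drug, patient request and the investigator's decision.

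**AE window.** Under SAP 5.1.2.1 the analysis uses treatment-emergent events, and the window closes "30 days after the last dose of study medication or until the start of new antitumor therapy, whichever comes first".

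**Expected difference.** Protocol 2.4 reports from phase II that "RR was highest at 66% for the S-1/LV/L-OHP group and PFS was 8.3 months", against 5.6 months for S-1/CDDP. Protocol 16.4 makes an assumption for this trial about OS only (hazard ratio 0.75).

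**Purpose.** Protocol 4.2 makes comparison of safety part of the secondary objective.

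**The concern.** The AE window closes soon after treatment stops, and treatment stops at progression. A regimen that delays progression therefore gives its patients more time in which an AE can be recorded. A crude proportion then mixes two things: how toxic the regimen is per month, and how many months it was taken. The mixing grows with any gain in disease control.

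At stake is the safety part of the secondary objective. If Arm A controls disease longer, part of an apparent excess of AEs could come from longer observation, and no planned AE frequency table would show how much. If Arm A is treated for less time, for example because of stopping for reasons other than progression, the distortion runs the other way and could hide toxicity.

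**Working it through.** The plan gives no AE rate, exposure or time-to-treatment-failure (TTF) figure to reproduce. What follows is an illustration under stated assumptions.

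**Inputs.** Median time on treatment m = 8.3 months (Arm A) and 5.6 months (Arm B), taken from the phase II PFS in Protocol 2.4. Assumed: PFS stands in for time on treatment; durations are exponential with μ = ln2/m; the AE hazard h per month is the same in both arms.

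**Step 1: AEs up to the last dose.** P = h/(h + μ).

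| h per month | Arm A | Arm B | Excess (points) | Excess if medians are 6 vs 5 months |
|---|---|---|---|---|
| 0.02 | 19.3% | 13.9% | 5.4 | 2.1 |
| 0.05 | 37.4% | 28.8% | 8.7 | 3.7 |
| 0.10 | 54.5% | 44.7% | 9.8 | 4.5 |

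**Step 2: add a one-month tail for the 30-day follow-up.** Mean time observed is m/ln2 + 1: 12.97 and 9.08 months, ratio 1.43. P = 1 − e^(−h)·μ/(μ + h). Choose h so that Arm B shows 30%: h = 0.0452.
- Arm B: μ = 0.1238; 1 − 0.9558 × 0.1238/0.1690 = 30.0%.
- Arm A: μ = 0.0835; 1 − 0.9558 × 0.0835/0.1287 = 38.0%.

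| Arm B proportion | 5% | 10% | 20% | 30% | 50% | 80% | 95% |
|---|---|---|---|---|---|---|---|
| Arm A proportion | 7.0% | 13.7% | 26.3% | 38.0% | 58.9% | 85.2% | 96.5% |
| Excess (points) | 2.0 | 3.7 | 6.3 | 8.0 | 8.9 | 5.2 | 1.5 |

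**Step 3: vary the assumptions.**
- Ratio of median durations, A to B, with Arm B at 30%: 1.25 gives +4.4 points, 1.10 gives +1.8, 1.00 gives 0, 0.90 gives −1.9.
- Hazard confined to the first 1, 2 or 3 months, durations 8.3 vs 5.6, Arm B at 30%: 0.0, 0.3 or 0.7 points. Over the whole range of Arm B proportions above, the largest such excess is 1.1 points.

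**Step 4: would person-time rates cure it?** Not for early AEs. In a simulation with h = 0.18 per month in both arms during the first two months only, and the durations of Step 2, the crude proportions almost agree (29.7% vs 29.4%). First-event rates are 0.0318 and 0.0445 per month, a ratio of 0.0318/0.0445 = 0.71. That falsely favours Arm A, because its extra months add time at risk but no events.

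**Step 5: would incidence at a common time cure it?** Largely. Within t months of first dose, with s = t − 1, P(t) = 1 − e^(−h)·[μ/(μ+h)·(1 − e^(−(μ+h)s)) + e^(−(μ+h)s)]. Here every close of the window counts as ending observation without the event. With the constant hazards of Step 2:

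| Arm B crude proportion | Excess, crude | Excess at 6 months | Excess at 70 days (t = 2.30) |
|---|---|---|---|
| 10% | 3.7 | 0.4 | 0.0 |
| 30% | 8.0 | 1.3 | 0.1 |
| 50% | 8.9 | 2.4 | 0.3 |
| 80% | 5.2 | 3.3 | 0.6 |

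The 70-day figure is almost free of the distortion, and the 6-month figure keeps a smaller part of it.

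**Step 6: is a usable time at risk already defined?** SAP 7.6.4 defines duration of TAS-118 and S-1 as number of doses divided by two, which is dosing days, and for the platinum drugs as number of doses. At full dosing Arm A takes drug on 7 of 14 days (50%) and Arm B on 21 of 35 (60%). Equal calendar time would therefore appear as a ratio of 0.50/0.60 = 0.83. SAP 7.6.7 does define a calendar duration, from the start of Cycle 1 to the last treatment.

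**The case against.** **Exposure is visible elsewhere.** TTF is a secondary endpoint, analysed by arm like OS (SAP 7.1.3). Cycle counts (7.6.6), laboratory grades by cycle (7.9) and days to onset of six clinical findings (7.10) are also planned. This stands in part: a reader could see that one arm was treated longer. None of these outputs adjusts an AE frequency, however. Per-cycle tables set two-week cycles against five-week cycles, and 7.10 names no method for censoring.

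**No between-arm AE test is listed.** True: Fisher's exact test and the Cochran–Mantel–Haenszel test are named for response and disease control. The arms will still be read side by side, because the objective is to compare safety.

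**The direction is not known.** This stands. A reader might infer that Arm A will necessarily look more toxic. The documents do not support that. They assume no PFS or TTF for this trial, progression is one of nine stopping criteria, and the sign reverses if Arm A is treated for less time.

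**Crude incidence is a legitimate measure of total burden.** This also stands, and is a reason to keep those tables.

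**The SAP is not the full list.** SAP section 9 says it gives representative analyses and leaves the rest to a separate output plan, which was not available. More may be planned there. The measure used to compare safety still belongs in the SAP.

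**Conclusion.** The point holds in a conditional form. AE frequency is described only as crude proportions, and the time over which AEs are counted depends on outcome. If time on treatment follows the phase II PFS and the AE hazard is constant and equal, Arm A's proportion could be too high by up to about 9 points (8.9 with the 30-day tail, 9.8 without it) for AEs of mid-range frequency. With medians of 6 versus 5 months the excess is 2.1 to 4.5 points at the hazards of Step 1. It is about 0 to 1 point for AEs confined to the first one to three months, 1.5 points for an AE at 95%, and negative if Arm A is treated for less time.

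Two stronger readings fail. The planned output does not leave unequal exposure hidden, because TTF and cycle counts would reveal it. Nor are person-time rate ratios a sound basis for the comparison, because they can mislead for early-onset toxicity. The primary OS analysis is not touched.

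**What to change.** In SAP 7.2.1:
1. Keep the crude tables and label them as total burden over treatment.
2. For grade 3 or higher AEs by preferred term, serious AEs and AEs leading to discontinuation, add the cumulative incidence of the first event by arm at common calendar times from first dose, for example 70 days and 6 months. Treat the end of the AE window by death or new therapy as a competing event. State also how a window that simply expires 30 days after the last dose is handled; Step 5 treats it in the same way.
3. Include the 70-day proportion. Seventy days is 5 × 14 and 2 × 35, so five Arm A and two Arm B cycles at nominal length only: Arm B recovery may be shortened and cycles may be delayed. Define the window in days, not cycles.
4. Exposure-adjusted first-event rates may be supplementary. Use calendar time from first dose to first event or the end of the AE window, built from treatment dates as in SAP 7.6.7 and not from the dose counts of 7.6.4. Note that they mislead for early-onset AEs, and base no comparative statement on them alone.

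The cost is SAP wording and a few tables from dates already collected. Early-window figures leave out late toxicity, which the crude tables still show.
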